The **secondary objective** is to evaluate 2 dose expansion cohorts after the maximum-tolerated dose (MTD) has been reached to better characterize the toxicity profile and identify early signs of efficacy. Our goal is to assess the anti-tumor activity Ribociclib + Tamoxifen and to further evaluate their safety in adult patients with HR+/HER2- locally advanced or metastatic breast cancer.

To determine whether treatment with ribociclib improves response rate (RR) compared to the historical response rate with treatment with Tamoxifen alone. We know that the expected RR for Tamoxifen after failure of first line AI is about 10 % and therefore we hypothesize an improvement of RR to 25%.

Efficacy Evaluation

Response and progression will be evaluated in this study using the new international criteria proposed by the Response Evaluation Criteria in Solid Tumors (RECIST 1.1). This will be expanded in protocol.

DEFINITIONS:

DLT – Dose-Limiting Toxicity

MTD – Maximum tolerated dose

PFS – Progression-Free Survival

DDI – Drug-Drug Interaction

ER – Estrogen Receptor

PR – Progesterone Receptor

HER2 – Human Epithelial Receptor 2

PO – by mouth (per orum)

SERMS (selective estrogen receptor modulators)

SOC – standard of care

RR- Response Rate

FIH – First in human

Protocol:

The TEEL Study: A Phase I trial of Tamoxifen with Ribociclib (LEE011) in adult patients with advanced ER+ (HER2 negative) breast cancer.

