4 INCLUSION CRITERIA

A. Shared Eligibility

1. Histologically and/or cytologically confirmed diagnosis of ER+ and/or PR+ breast cancer by local laboratory.
2. HER2-negative breast cancer defined as a negative in situ hybridization test or an IHC status of 0, 1+ or 2+. If IHC is 2+, a negative in situ hybridization (FISH, CISH, or SISH) test is required by local laboratory testing.
3. Patients are allowed (but not required) to have up to **two** lines of prior chemotherapy regimens in the metastatic setting for the dose expansion phase (). For the dose escalation cohort, up to three previous lines of chemotherapy in the metastatic setting is acceptable.
4. Measurable disease, i.e., at least one measurable lesion as per RECIST 1.1 criteria only **for expansion cohorts**.

5. For **escalation cohorts**, bone only disease is allowed. For expansion cohorts, there must be measurable disease as stated above (#4)..
6. ECOG PS 0 or 1.
7. Written informed consent must be obtained prior to any screening procedures and according to local guidelines.
8. Patient has adequate bone marrow and organ function as defined by the following laboratory values:
 - a. Absolute neutrophil count $\geq 1.5 \times 10^9/L$.
 - b. Platelets $\geq 100 \times 10^9/L$.
 - c. Hemoglobin $\geq 9 \text{ g/dL}$.
 - d. Potassium, total calcium (corrected for serum albumin), magnesium, and sodium within normal limits for the institution or corrected to within normal limits with supplements before first dose of study medication
 - e. INR ≤ 1.5 .
 - f. Serum creatinine $\leq 1.5 \times \text{ULN}$ or creatinine clearance $\geq 50 \text{ mL/min}$
 - g. In the absence of liver metastases, alanine aminotransferase (ALT) and aspartate aminotransferase (AST) $< 2.5 \times \text{ULN}$. If the patient has liver metastases, ALT and AST $< 5 \times \text{ULN}$.
 - h. Total bilirubin $\leq \text{ULN}$; or total bilirubin $\leq 3.0 \times \text{ULN}$ or direct bilirubin in patients with well-documented Gilbert's Syndrome
9. Must be able to swallow ribociclib and Tamoxifen capsules/tablets

B. Pre-menopausal Women Eligibility

1. Premenopausal women who received adjuvant Aromatase Inhibitor and Ovarian Suppression (AI + OS) in the adjuvant setting and completed at least 12 months of hormonal therapy.
2. Pre-menopausal women with *de novo* metastatic disease are eligible if they have had no prior endocrine therapy.

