8.6 Efficacy Evaluation for Dose I Expansion Cohorts:**Imaging tumor assessments:**

Tumor response will be assessed according to RECIST Version 1.1 (Eisenhauer et al 2009). Patients should have at least one documented measurable lesion (per RECIST v1.1) or in the absence of measurable disease, have at least one predominantly lytic bone lesion at study entry.

Imaging assessments will be performed at screening within 28 days prior to randomization and subsequently every 8 weeks during the first 12 months and every 12 weeks thereafter. See Table 1-2 for details of assessments.

The 8-week (or 12 week) interval should be respected regardless of whether study treatment is temporarily withheld. After baseline, all assessments should be performed within \pm 7 days of the scheduled day of assessment. The same method of assessment and the same technique should be used to characterize each individual and reported lesion at baseline and during follow up.

If a patient discontinues treatment for reasons other than radiological documentation of progression of disease, an efficacy assessment should be performed at the time of End of Treatment unless a CT/MRI for tumor measurement was performed within 21 days.

All patients will undergo CT or MRI of the chest, abdomen and pelvis at baseline and subsequent scheduled visits per Table 1-2. The preferred imaging methodology is CT with intravenous (i.v.) contrast. However, if at baseline, a patient is known to have a contraindication to CT i.v. contrast media or develops a contraindication during the trial, a non-contrast CT of chest (MRI is not recommended due to respiratory artifacts) plus contrast-enhanced MRI (if possible) of abdomen and pelvis should be performed.

A whole body bone scan or FDG-PET should be acquired at baseline for all subjects. Skeletal lesions identified on the whole body bone scan at baseline, which are not visible on the chest, abdomen and pelvis CT (or MRI) scan should be imaged at baseline and followed at scheduled visits using localized CT, MRI or x-ray. Whole body bone scans need not be repeated after baseline unless clinically indicated.

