10.2 Statistical Considerations for Phase Ib Dose expansion Study

If no MTD is observed with Level 1 through 3, we plan to continue/conduct the phase Ib dose expansion study as below. This expansion study is planned to understand and obtain initial efficacy data for the secondary endpoints.

Since the identical patient inclusion/exclusion criteria will be used in phase Ib dose expansion, all patient data from phase I dose escalation and phase Ib dose expansion studies can be combined for our statistical analysis, therefore, the required sample size of patients below will be both for phase I dose escalation and phase Ib dose expansion studies.

We obtained our statistical power and required sample size as a single-arm prospective study. In particular, for our evaluation of early efficacy we designed the study particular, for our evaluation of early efficacy we designed the study for testing $H_0: P \leq 0.10$ versus $H_1: P \geq 0.25$ at one-sided significance level 0.05 and power 0.80 as below.

P0	P1	Alpha	Beta	Cut-Off		Actual	Actual
				R + 1	N		
0.100	0.250	0.050	0.200	8	40	0.042	0.182

Where P0 is the maximum response proportion of standard care (tamoxifen alone), P1 is the minimum response proportion of our experimental treatment group, and N is the sample size.

For our statistical testing, if the number of responses $\geq R+1$, P0 is rejected based on Fisher's Exact test (34, 35). Alpha is the probability of rejecting that $P \leq P_0$ when this is true.

Beta is the probability of rejecting that $P \geq P_1$ when this is true.

Thus, the study requires 6 subjects under phase I dose escalation and 30 subjects under phase Ib dose expansion who will be treated with ribociclib (total 36) in order to test whether the proportion responding, P, is less than or equal to 0.100 or greater than or equal to 0.25. If the number of responses is 8 or more, the hypothesis that $P \leq 0.100$ is rejected with a target Type I error rate, α , of 0.050 and an actual error rate of 0.045. The null hypothesis will be rejected if 8 or more responses are observed in 40 patients. This design yields a type I error rate of 0.045 and power of 0.818 when the true response rate is 0.25.

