11.1 Criteria for Target Lesions

11.1.1 *Measurable disease*

Measurable lesions are defined as those that can be accurately measured in at least one dimension (longest diameter to be recorded) as ≥ 20 mm with conventional techniques (CT, MRI, x-ray) or as ≥ 10 mm with spiral CT scan. All tumor measurements must be recorded in millimeters (or decimal fractions of centimeters).

11.1.2. *Non-measurable disease*

All other lesions (or sites of disease), including small lesions (longest diameter < 20 mm with conventional techniques or < 10 mm using spiral CT scan), are considered non-measurable disease. Bone lesions, leptomeningeal disease, ascites, pleural/pericardial effusions, lymphangitis cutis/pulmonis, inflammatory breast disease, abdominal masses (not followed by CT or MRI), and cystic lesions are all non-measurable.

11.1.3. *Target lesions*

- All measurable lesions up to a **maximum of two lesions per organ** and **five lesions in total**, representative of all involved organs, should be identified as target lesions and recorded and measured at baseline.
- Target lesions should be selected on the basis of their size (lesions with the longest diameter) and be representative of all involved organs, as well as their suitability for reproducible repeated measurements.
- All measurements should be recorded in metric notation using calipers if clinically assessed. A **sum of the diameters (longest for non-nodal lesions, short axis for nodal lesions)** for all target lesions will be calculated and reported as the baseline sum diameters, which will be used as reference to further characterize any objective tumor regression in the measurable dimension of the disease. If lymph nodes are to be included in the sum, only the short axis will contribute.

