11.6 Evaluable disease

Patients must have measurable disease for dose expansion phase. Patients with bone only disease for this protocol are eligible if at least one lesion can be measured by MRI that is measurable by RECIST 1.1. Tumor markers are not considered measurable.

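### Section 8.6 admits expansion patients on a lytic bone lesion alone, against inclusion criteria A.4/A.5, and Sections 11.6 and 11.1.2 disagree on whether a bone lesion can be measurable

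*Combined protocol and SAP*

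**What the plan says.** **Entry to expansion.** Inclusion criterion A.4 requires at least one RECIST 1.1 measurable lesion in the expansion cohorts. A.5 allows bone-only disease in escalation and then says: "For expansion cohorts, there must be measurable disease as stated above". The first sentence of Section 11.6 repeats this requirement.

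**Section 8.6.** Under a heading for the expansion cohorts, it asks for one measurable lesion or accepts patients who "in the absence of measurable disease, have at least one predominantly lytic bone lesion at study entry".

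**Bone lesions as measurable disease.** Section 11.6 goes on: "Patients with bone only disease for this protocol are eligible if at least one lesion can be measured by MRI". It adds the condition that the lesion be measurable under RECIST 1.1. Section 11.1.2 gives a list of non-measurable disease that begins "Bone lesions, leptomeningeal disease, ascites, pleural/pericardial effusions" and makes no exception for any kind of bone lesion.

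**Response.** Target lesions are chosen from measurable lesions (11.1.3). Partial response is a fall of at least 30% in the target-lesion sum (11.2.1). The non-target categories in 11.2.2 are complete response, incomplete response/stable disease and progression.

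**The test.** Section 10.2 pools escalation and expansion patients. It sets the test at "one-sided significance level 0.05 and power 0.80 as below", with this rule: "The null hypothesis will be rejected if 8 or more responses are observed in 40 patients".

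**The concern.** Two sets of passages need reconciling.

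First, A.4/A.5 and 8.6 describe the same cohorts at the same moment, study entry, and give opposite answers for a patient whose only disease is a lytic bone lesion. Section 8.6 cannot be explained as serving the escalation patients, because A.5 already admits them with bone-only disease and sets no lytic condition.

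Second, 11.6 and 11.1.2 disagree on whether a bone lesion can ever be measurable, and so on whether a partial response can be called on one.

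Objective response is the only efficacy measure with a decision rule. An expansion patient admitted under 8.6 stays in its denominator: 10.2 defines no response-evaluable set based on measurable disease, and 11.3 replaces only early deaths and patients with no follow-up assessment. Such patients lower the observed rate for a reason unrelated to drug activity.

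**Working it through.** **Step 1. Follow one patient through the text.** Take an expansion candidate with a lytic bone lesion and no other disease.

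- A.4, A.5 and the first sentence of 11.6: ineligible unless the lesion counts as measurable.
- 8.6: acceptable.
- If enrolled, 11.1.2 makes the lesion non-measurable. Under 11.1.3 there is then no target lesion, and partial response under 11.2.1 cannot be reached.
- Complete response through disappearance of all non-target lesions is still defined in 11.2.2. The best-response table in 11.3 has no row for a patient with no target lesions, no progression and no new lesion.
- If the second sentence of 11.6 is followed and the lesion is judged measurable on MRI, it can be a target lesion and partial response is possible.

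**Step 2. Reproduce the plan's figure.** Inputs: null rate 0.10 and target rate 0.25 (synopsis: "expected RR for Tamoxifen after failure of first line AI is about 10 % and therefore we hypothesize an improvement of RR to 25" percent; also 10.2), N = 40 and cut-off 8 (10.2). With X ~ Binomial(40, p):

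- Type I error = P(X ≥ 8 | p = 0.10) = 0.0419
- Power = P(X ≥ 8 | p = 0.25) = 0.818

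These match the table in 10.2 (0.042, and beta 0.182). The accompanying text reads: "This design yields a type I error rate of 0.045 and power of 0.818 when the true response rate is 0.25". Its power agrees; its 0.045 does not reproduce.

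**Step 3. Add patients who cannot respond.** The documents give no bone-only fraction, so k is an assumption. If k of the 40 have zero response probability and the cut-off stays at 8, then X ~ Binomial(40 − k, p):

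| k | Average true rate, 0.25 × (40 − k)/40 | Power | Type I error |
|---|---|---|---|
| 0 | 0.250 | 0.818 | 0.042 |
| 1 | 0.244 | 0.795 | 0.037 |
| 3 | 0.231 | 0.741 | 0.027 |
| 5 | 0.219 | 0.678 | 0.020 |

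One such patient takes power below the planned 0.80.

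**Step 4. Allow for complete response.** If each of these patients has an assumed 5% chance of complete response, power at k = 4 is 0.734 rather than 0.710. The loss is smaller but remains.

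**Step 5. Ask whether correcting 8.6 is enough.** It is not. A.5 allows bone-only disease in escalation, and 10.2 pools those patients on the stated premise that the two phases share identical criteria. Section 10.2 counts 6 escalation patients and the synopsis 9–12. Any of them without measurable disease acts on the test in the same way as k above.

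**The case against.** The strongest reply is that enrolment follows the eligibility criteria. Measurable disease for expansion is stated three times (A.4, A.5, 11.6), against one sentence in an imaging section. That section also refers to randomization in a non-randomized study, which suggests carried-over text. One centre is planned at the start, so differing practice between sites is not the present situation. This stands as to likelihood: few expansion patients would probably enter this way. It does not remove the contradiction.

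Three stronger readings are tempting, and the documents do not support them.

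- **That 11.6 is a second route for patients who cannot have a partial response.** If 11.1.2 governs, no bone lesion meets the 11.6 condition and it admits nobody on bone alone. If the RECIST 1.1 condition in 11.6 governs, the lesion can be a target lesion and partial response is possible. The conflict of 11.6 is with 11.1.2, not with A.4/A.5.
- **That power could fall to about one half.** At k = 10 it would be 0.486, but through 8.6 alone that means 10 of 30 expansion patients enrolled against an explicit inclusion criterion. Nothing in the documents suggests this.
- **That these patients cannot respond at all, or that the error favours the drug.** Complete response remains possible, and dilution lowers type I error along with power.

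It is also fair to say that the main aim is safety, DLT and the RP2D. The synopsis places response under the secondary objective, and 10.2 describes the expansion as giving initial efficacy data for secondary endpoints. This limits the severity.

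**Conclusion.** The concern holds in a limited form. Section 8.6 contradicts A.4/A.5 and the first sentence of 11.6 on entry to expansion. Separately, 11.6 and 11.1.2 contradict each other on whether a bone lesion can be measured.

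A patient admitted under 8.6 cannot have a partial response under 11.1.2–11.2.1 but counts in the 8-of-40 test. With an assumed 1, 3 or 5 such patients, power is 0.795, 0.741 or 0.678 instead of 0.818. These figures assume a true rate of 25% in all other patients, a fixed cut-off of 8 and no complete responses among the k; the loss is somewhat smaller if complete responses occur. The direction is conservative. The effect of partial responses called on bone lesions under 11.6 cannot be sized from the documents.

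Severity: should be fixed. The harm is a loss of power and an unclear denominator on a secondary endpoint. No safety rule or primary analysis is affected.

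**What to change.** 1. **Section 8.6:** remove the lytic-bone alternative for the expansion cohorts, so that it agrees with A.4/A.5.
2. **Sections 11.6 and 11.1.2:** state in both, in the same words, whether any bone lesion can be a target lesion and under what condition.
3. **Section 10.2:** restrict the response test to patients with measurable disease at baseline, whether from escalation or expansion, and restate N, cut-off and power for that set. In the same edit, settle the total (36 or 40) and the type I error (0.042 or 0.045).

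**Cost.** Items 1 and 2 are wording only, at the price of a few bone-only patients not enrolled in expansion. They are best made before expansion patients enter, because a patient without measurable disease cannot be given it later.

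Item 3 makes the rate interpretable but does not by itself restore power. Forty is the smallest single-stage N that meets type I error of at most 0.05 and power of at least 0.80 for these rates, so 0.818 needs 40 measurable patients. If 36 are measurable, the cut-off must stay at 8 (7 of 36 gives type I error 0.063) and power is 0.710. If only the 30 expansion patients qualify, 7 of 30 gives type I error 0.026 and power 0.652. The sponsor should either enrol to 40 measurable patients or state the lower power.

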8.7 Treatment Duration

Eligible patients will receive treatment as described above, in consecutive 4-week cycles, until progression of disease or unacceptable toxicity. Patients are expected to receive treatment for at least 2 cycles, at which time the first evaluation for efficacy will occur. If there is continued safety and tolerability in the absence of any documented disease progression, treatment may continue for 2 years or until progression or non-tolerance.

Patients will be followed for evaluation of safety for at least 30 days after the last dose of study drug. Any study drug-related serious adverse events will be followed until resolution, return to baseline grade, or deemed irreversible by the Investigator.

9 PHARMACOKINETICS

PK blood samples will be obtained from all patients in both the phase I dose escalation and Ib dose expansion (when feasible) for the analysis of plasma concentrations of ribociclib (and any relevant metabolites such as LEQ803) and tamoxifen (and any relevant metabolites such as N-desmethyltamoxifen, 4-hydroxytamoxifen, and endoxifen) to evaluate any potential DDI. PK blood samples will be collected at steady-state on Cycle 3 Day 15 & 16 at pre-dose, 0.5, 1, 2, 4, 8 and 24 hrs post dose to allow for evaluation of exposure-response (efficacy endpoints and/or safety endpoints) relationships.

Steady-state for RIBOCICLIB, Tamoxifen (and metabolites), is generally achieved after daily dosing for 8 days, 4-8 weeks, 14-40 days, and 7 days, respectively; therefore, an assessment on Cycle 3 Day 15 is considered appropriate to evaluate steady-state PK.

Plasma concentrations of RIBOCICLIB and Tamoxifen will be determined by the Clinical Pharmacology Laboratory of the Translational Research Core at the Moffitt Cancer Center using LC/MS/MS methods that are validated according to ICH/FDA guidelines for bio-analytical analysis.

Tamoxifen with ribociclib will be compared to historical single agent ribociclib PK data, if feasible. If a patient discontinues from the study treatment due to toxicities related to study treatment, an unscheduled PK blood sample may be obtained as soon as possible after the last dose and the date and time of last dose recorded. In addition, an unscheduled blood sample may be collected if additional ECG measurements are conducted.

The date and exact time of dosing on PK collection days, as well as the date and actual time of blood sampling must be recorded on the appropriate eCRF pages and PK requisitions. In addition, the exact time of dosing on the previous day must be precisely recorded. Any sampling problems (e.g., patient took study drug before blood sample, scheduled sampling time is missed, sample is not drawn according to the schedule) should be noted as a comment on the eCRF.

If vomiting occurs during the course of treatment, no “re-dosing” of the patient is allowed, and medication should resume on the next day. The occurrence and frequency of any vomiting must be noted in the adverse events section of the eCRF. In addition, the date and exact time of vomiting should only be recorded if it occurs within 4 hours of dosing on the days of full PK sampling. If a vomiting episode occurs within the first 4 hours post-dosing during the day of the last dose prior to trough PK sample the exact time (whenever possible) must be noted on the eCRF.

PK parameters, such as Cmax, Tmax, and AUC0-24h, will be estimated (when feasible) from individual plasma concentration-time profiles using appropriate methods and software (Phoenix WinNonlin® ver6.3).

10 STATISTICAL CONSIDERATIONS

10.1 Statistical Considerations for Phase I Study

A standard 3+3 design will be used (33) for the primary toxicity study under Phase I. A cohort of 3 patients will be recruited for each dose level at a time at a time. The first dose level will be level 1 and gradually increased to Level 2 and 3 if toxicity AEs are observed within the predefine statistical criterion/limit below.

Level 1: Ribociclib PO starting at a dose of 400 mg po for 21 days, followed by 1 week break of a 28-day treatment cycle;

Level 2: Ribociclib PO treated with a dose of 400 mg po daily for 28 days;

Level 3: Ribociclib PO treated with a dose of 600 mg po for 21 days, followed by 1 week break of a 28-day treatment cycle

If 1 patient out of 3 experiences a dose limiting toxicity (DLT; see below for definition) at level 1, 3 additional patients will be recruited at that dose level. If only 1 out of 6 patients in that dose level experiences a DLT, a new cohort of 3 patients will be treated with the next escalated dose level. That is, the dose escalation continues until at least two patients among a cohort of three to six patients experience dose-limiting toxicities (i.e., $\geq 33\%$ of patients with a dose-limiting toxicity at that dose level). If 2 out of 3 or 2 out of 6 patients experience a DLT, no further dose escalation will occur. The recommended phase II dose (RP2D) is defined as the dose level at which $\leq 1/6$ patients experience DLT. There will be no dose escalation beyond dose level 3, meaning that if $\leq 1/6$ patients experience DLT at this level, dose level will become the RP2D. No intra-patient dose escalation is allowed. Our dose escalation schedule follows a modified Fibonacci sequence in which the dose increments become smaller as the dose increases (e.g., the

dose first increases by 100% of the preceding dose, and thereafter by 50%, 33%, and 25% of the preceding doses). The RP2D will be defined as the dose level just below this toxic dose level.

Patients who achieve complete response (CR) or partial response (PR) or have stable disease (SD) may continue on study treatment until disease progression, as defined by RECIST v1.1 criteria, or intolerable toxicity.

